3.3.2 For Partial End Dates

- 1. If the year is unknown, then do not impute the date but assign a missing value.
- 2. If the month is unknown, then assign "December."
- 3. If the day is unknown, then assign the last day of the month.

After implementing the rules above, to determine whether AEs (or medications) with missing start or stop dates are pre-treatment or on/after treatment, the following strategy will be used:

- 1. If both start date and stop date are missing, then the most conservative approach is taken, and the AE (or medication) is considered to be treatment emergent (or concomitant medication).
- 2. If the start date is missing but the stop date is not missing and is on or after the day of study dose administration, then the most conservative approach is taken, and the AE (or medication) is considered to be treatment emergent (or concomitant medication).
- 3. If the start date is missing but the stop date is not missing and is before the day of study dose and after the date of signed informed consent, then the AE (or medication) is considered to be before treatment (or prior medication).
- 4. If the start date is not missing but the stop date is missing, then the most conservative approach is taken, and medication is considered to be concomitant while the AE is defined by start date.

3.4 Study Day

The study day for each assessment/event of a subject will be derived using their first study drug administration date. For the assessments performed on or after first study drug administration date, study day is calculated as

Study Day = (Date of assessment/event – Date of first study drug administration) + 1

For the assessments performed prior to first study drug administration, study day is calculated as

Study Day = (Date of assessment/event – Date of first study drug administration)

The summary and analysis will be performed considering the different timepoint when the assessment was conducted.

CONFIDENTIAL Page 16 of 31

Private and Confidential Study No 21755 Date: DEC 18, 2023

3.5 Statistical Significance & Multiplicity

All analyses will be based on two-tailed testing at significance level (alpha) of 0.05. No multiplicity adjustment will be made for analyzing efficacy endpoints.

4 DEFINITIONS AND DERIVATIONS

Run-in Failures: Run-in failures are participants who successfully completed screening and randomized to a blinded study intervention (treatment). Participants start a 6-month eligibility window during the Run-in Phase where they could potentially self-initiate treatment. Participants who are considered a Run-in failure occur because of the following:

- Randomized participants with no prodromal symptoms after 6 months
- Met an exclusion criterion (e.g., medication, pregnancy)
- Adverse event or change in medical history that requires study withdrawal
- Withdraw of informed consent by the participant
- Study intervention kit not available
- Lack of compliance as determined by the Investigator/designee

Baseline: Baseline value is defined as the last non missing assessment prior to first administration of the study drug. If the assessment occurs on the same day as the first study drug administration, then the time of assessment should be compared to the time of first dose administration to derive the baseline value.

Post-baseline: The Post-baseline values are defined as assessments taken after the first administration of study drug/treatment.

Change from Baseline = $(post\ baseline\ value - baseline\ value)$.

Duration of Episode (DOE): DOE is defined as the time from the initiation of treatment to the healing of primary lesions (loss of crust) for subjects who experience a vesicular lesion. For subjects whose primary lesions are not vesicular in nature, DOE is the time from study intervention initiation to the return to normal skin as determined by the independent blinded reader of the subject's face images using a 6-point Likert scale or the cessation of symptoms, whichever comes last. For the subjects who do not demonstrate the healing of primary lesions or cessation of symptoms, the data will be censored at 14 days (14*24 hours) regardless of any circumstances. If time (hour) is missing for either treatment initiation or the healing of primary lesion or both, however, both dates are recorded, then DOE is number of days (end date – start date) *24. If only healing ending date and/or time are missing, DOE will be imputed as 14*24 hours. If date of treatment initiation is missing, then DOE will be missing.

CONFIDENTIAL Page 17 of 31

Private and Confidential Study No 21755 Date: DEC 18, 2023

DOE (hours) = (Date and time of healing of primary lesions – Date and time of first treatment administered)

Vesicular lesion: A lesion will be categorised as vesicular if a subject has face image interpretation Likert scale score of 3 or above.

Healing of primary lesions: A vesicular lesion will be considered as healed if the face image interpretation Likert score drops to either 0 or 1 after progressing to 3 and beyond. For those without a vesicular lesion, healing is defined as a face image interpretation Likert score of 0 or cessation of symptoms i.e., all NRS symptom scores as 0, whichever comes last.

Cessation of symptoms: Cessation of symptoms is defined as the absence of sensations of pain, tenderness tingling, itching or discomfort at the site of the cold sore as measured by NRS. In other words, having the NRS score of 0 for all symptoms such as pain, tingling, tenderness, itching and discomfort is cessation of symptoms.

Time to cessation of symptoms: It is the time (in hours) from the initiation of treatment dose of assigned study intervention to cessation of symptoms. For the subjects who do not demonstrate the cessation of symptoms, the data will be censored at 14 days (14*24 hours) regardless of any circumstances. If hour is missing for either treatment initiation or the endpoint but both dates are recorded, then Time to cessation of symptoms is number of days (end date – start date) multiplied by 24. If either date is missing, then Time to cessation of symptoms is missing.

 $\it Time\ to\ cess at ion\ of\ symptoms = (Date\ and\ time\ of\ cess at ion\ of\ symptoms - Date\ and\ time\ of\ first$

treatment administered)

Time to recurrence of HL lesions: It is the time (in days) from resolution of the cold sore treated in the Treatment phase until appearance of a cold sore during the follow-up period. The time to first recurrence is determined by assessment from the investigator and documented using NRS symptom scores and face images using the Science 37 Platform. For subjects who do not recur during the follow-up period, the data will be censored at the time of last follow-up.

Time to recurrence of HL lesions (Days) = (Date of first recurrence of HL lesions – Date of healing of primary lesions) + 1

CONFIDENTIAL Page 18 of 31

Private and Confidential Study No 21755 Date: DEC 18, 2023

Treatment Emergent Adverse Event: A TEAE is defined as any new AE that commences on or after the start of the first study drug administration or any pre-existed AE/ condition that worsened in severity following administration of study drug.

End of Treatment Phase: The end of the Treatment Phase for a subject is defined as the date (time) of the last visit in the Treatment Phase.

End of Study: The end of the study is defined as the date of the last follow-up visit (either by documented HL outbreak or at 12 months) of the subject in the study. A subject is considered to have completed the study if he/she has completed all phases of the study up to Follow up Phase.

Aborted Lesion: It is defined as a treated HL lesions that do not progress to the vesicular or crust stage. A lesion that returns to normal skin without forming a vesicle or crust will be counted as an aborted lesion i.e., for this lesion the face image interpretation Likert score will be less than or equal 2 and will never reach a score of 3 or above before healing.

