9.4.2 Primary Endpoint

The primary efficacy variable is:

• Duration of episode (DOE) will be measured in hours (using the Science 37 Platform), of a single treated HL lesion. Observation period to determine healing will last up to 14 days (DurEp14).

Duration of episode (DOE) is defined as the time from the initiation of treatment (study intervention) to the healing of primary lesions (loss of crust) for participants who experience a vesicular lesion. For participants whose primary lesions are not vesicular in nature, duration of episode is the time from study intervention initiation to the return to normal skin as determined by the independent blinded reader of the participant's face images using a 6-point Likert scale or the cessation of symptoms, whichever comes last. For the subjects who do not demonstrate the healing of primary lesions or cessation of symptoms, the data will be censored at 14 days (14*24 hours) or time of loss of follow-up, whichever happens earlier.

Duration of episode (DOE) will be estimated and plotted using Kaplan-Meier method and analyzed using log-rank test.

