9.4.4 Other Endpoints

- Duration of episode (DOE) will be measured in hours (using the Science 37 Platform), of a single treated HL lesion in participants who initiation study intervention within 1 hour of onset of prodromal symptoms and participants who initiated study intervention more than 1 hour after onset of prodromal symptoms.
- Time to cessation of symptoms, measured in hours from the 1st dose of assigned study intervention. Cessation of symptoms is defined as the absence of sensations of pain, tingling, or burning at the site of the cold sore. Observation period to determine healing will last up to 14 days (CesSymp14).
- Quality of life score, as measured by the OHIP-14 questionnaire at 3, 7 and 14 days post-dose will be analyzed using CMH method with a modified ridit score.
- Global assessment of treatment efficacy at Day 14 using a 5-point scale (0=none, 1=poor, 2=fair, 3=good, 4=excellent) will be analyzed using CMH method with a modified ridit score.

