3.3 Handling of Missing Data

For subjects whose HL lesions are healed, however, healing ending date and time are missing, DOE and time to cessation of symptoms will be imputed as 14*24 hours since the observation period to determine healing can last up to 14 days.

To handle missing or partial dates, the following rules will be applied.

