7.7.3 Analysis of Other Efficacy Endpoints

The analysis of other endpoints will be performed on ITT population.

- **Duration of episode (DOE)** will be measured in hours (using the Science 37 Platform), of a single treated HL lesion in subjects who initiate study intervention within 1 hour of onset of prodromal symptoms and subjects who initiated study intervention more than 1 hour after onset of prodromal symptoms. DOE will be analyzed similarly to the analysis of primary efficacy endpoint using KM method. Individual subject data Listing for DOE will be presented.
- Fine to cessation of symptoms, measured in hours from the initiation of first dose of study drug. Cessation of symptoms is defined as the absence of sensations of pain, tingling, or burning at the site of the cold sore. Observation period to determine healing will last up to 14 days. Time to cessation of symptoms will be analyzed similarly to the analysis of primary efficacy endpoint using KM method. Individual subject data listing for Time to cessation of symptoms will be presented.
- ➤ Quality of life score, as measured by the OHIP-14 questionnaire at 3-, 7- and 14-days post-dose will be analysed using Cochran-Mantel-Haenszel (CMH) method with a modified ridit score. The number and percentage of subjects will be summarized for each question/item in OHIP-14 questionnaire by scheduled visits and treatment groups. The actual values of OHIP-14 weighted score for subscale category questions will be summarized by scheduled visits and treatment groups. The post-dose values will be compared between the Sitavig and placebo groups using two sample t-test assuming the normality of data and if the data is non-normal then Wilcoxon Rank-Sum test (also known as the Mann-Whitney U test) will be used. Please refer the Section 9.2 in this SAP for weight factors associated with subscale category questions. Individual subject data listing for OHIP-14 will be presented.
- ➤ Global assessment of treatment efficacy at Day 14 using a 5-point scale (0=none, 1=poor, 2=fair, 3=good, 4=excellent) will be analysed using CMH method with a modified ridit score. The number and percentage of subjects will be summarized for Global assessment of treatment efficacy. Individual subject data listing for Global evaluation will be presented.

CONFIDENTIAL Page 24 of 31

Private and Confidential Study No 21755 Date: DEC 18, 2023

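### The SAP censors DOE at 336 h even for dropouts, an undeclared contradiction of protocol 9.4.2, and its missing-date rules conflict with one another

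*SAP*

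**What the plan says.** **DOE censoring.** Protocol 9.4.2 states that for participants who do not heal "the data will be censored at 14 days (14*24 hours) or time of loss of follow-up, whichever happens earlier". SAP Section 4 replaces this, for participants who do not demonstrate "healing of primary lesions or cessation of symptoms, the data will be censored at 14 days (14*24 hours) regardless of any circumstances". SAP 7.13, which lists changes from the protocol, names only the recurrence-incidence test.

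**Time to cessation of symptoms.** SAP Section 4 repeats the fixed horizon: "For the subjects who do not demonstrate the cessation of symptoms, the data will be censored at 14 days (14*24 hours) regardless of any circumstances". Protocol 9.4.4 defines the endpoint ("Time to cessation of symptoms, measured in hours from the 1st dose of assigned study intervention") with a 14-day observation period but gives no censoring rule.

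**Missing dates.** SAP 3.3 begins "For subjects whose HL lesions are healed, however, healing ending date and time are missing" and then imputes 14*24 hours for both endpoints. SAP Section 4 has its own sentences. For DOE, when both dates are recorded but an hour is missing, the value is the difference in dates times 24. The next sentence reads "If only healing ending date and/or time are missing, DOE will be imputed as 14*24 hours". For time to cessation it says "If either date is missing, then Time to cessation of symptoms is missing".

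**Populations.** Under SAP 6.1, ITT entry needs one post-dose face-image score, and PP requires completion of 14 days of evaluations. PP is primary for DOE, with ITT repeated as the robustness check. SAP 7.7.3 adds "The analysis of other endpoints will be performed on ITT population", which covers DOE by start within or after 1 hour and time to cessation.

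**The concern.** Kaplan-Meier, log-rank and Cox estimates assume that each person counted at risk at a given time was still under observation then. Under the SAP rule, a participant whose last image is on Day 3 is carried as known to be unhealed for about 11 further days. That participant can no longer contribute an event but still counts in every later denominator.

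The ITT analysis of DOE exists to test whether the PP result is robust. If ITT handles dropouts in this way, agreement or disagreement with PP may reflect dropout handling instead of drug effect. The two ITT-only endpoints have no PP counterpart to compare with.

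The conflicting missing-date sentences raise a second problem: two programmers following the SAP faithfully could build different datasets.

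**Working it through.** **1. The SAP's figure.** 14*24 = 336 h. The last scheduled Day 14 image is at 19:00 with a 60-minute window, so its latest time after dosing is 13*24 + 20 − (clock hour of dosing). This is 332 h for dosing at 00:00 and about 308 h for dosing just before midnight (331 and 307 h without the window). So 336 h lies beyond every scheduled image.

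**2. The two DOE rules side by side.** For a participant lost at time L < 336 h before healing, the protocol gives (L, censored) and the SAP gives (336, censored). The SAP wording leaves no room for the loss-to-follow-up limb. The SAP does not follow this practice throughout: for time to recurrence it censors at last follow-up.

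**3. Direction of the effect.** Kaplan-Meier uses the product of (1 − d_j/n_j), and the log-rank expectation for one arm is d_j·n_1j/n_j. Keeping dropouts inflates n_j.
- Equal loss: both curves are lifted and the hazard ratio moves toward 1.
- Unequal loss: the arm with more loss has the more inflated n, so its healing looks slower.

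**4. Size, by simulation.** From the documents: two-sided 0.05, 1:1 allocation, cap 336 h, usual duration 7 to 10 days (7*24 = 168 h to 10*24 = 240 h, protocol Section 2), and an earlier trial's 0.57-day reduction (0.57*24 = 13.68 h; protocol 2.2, primary-lesion healing and not DOE). Assumed: Weibull shape 2, 200 per arm, exponential withdrawal independent of healing, with the stated share gone by 336 h. Both rules were applied to the same simulated datasets. Hazard ratios are active versus placebo for healing, so values above 1 favour active.

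Rejection with no drug effect, SAP rule:

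| Loss, active vs placebo | Median 168 h | 204 h | 240 h |
|---|---|---|---|
| 3% vs 5% | 5.2% | 5.5% | 5.8% |
| 5% vs 15% | 20.2% | 16.6% | 13.9% |

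The protocol rule gives about 5% in these cells.

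Power for a 0.57-day benefit at a 204 h median, protocol rule to SAP rule:
- equal 3% loss: about 25% to 24%;
- equal 10% loss: about 23% to 21%.

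**5. A second set of assumptions** (300 per arm, median 168 h, dropout times uniform over 0–336 h).
- No drug effect, 5% vs 15%: 24.5% rejection (HR 1.12) under the SAP rule against 4.9% under the protocol rule. Reversed, 15% vs 5%: 26.9% (HR 0.89) against 5.6%.
- Equal loss of 5%, 10% and 20%: type I error under the SAP rule stays at 4.6–6.0%. For the 0.57-day benefit, the hazard ratio falls from 1.19 to 1.17, 1.16 and 1.14. Power is 46%, 41% and 32%, against 51%, 49% and 47% under the protocol rule.
- No loss: the two rules are identical.

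**6. Extreme loss model.** If the whole stated share is lost before healing, 5% vs 15% gives 62% to 32% rejection over the same medians (200 per arm). Loss then depends on healing, and the protocol rule is slightly biased too (HR about 1.04, rejection about 6–7%).

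**7. Missing-date conflicts.**
- *Healed participant with no recorded end date, time to cessation:* SAP 3.3 gives 336 h; Section 4 gives missing.
- *DOE, healing on Day 7, both dates recorded, healing hour missing:* the missing-hour sentence gives (7 − 1)*24 = 144 h. The next sentence also covers a missing time and gives 336 h. The gap is 336 − 144 = 192 h. A PP participant can fall into this case.
- Neither SAP 3.3 nor Section 4 says whether an imputed 336 h counts as an event or as censored.

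**The case against.** **The primary analysis is barely touched.** This stands. A reader might infer that the primary DOE result is compromised by the censoring rule. The documents do not support that, because PP requires 14 days of evaluations and so removes most dropouts.

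**Loss may be small.** Protocol 7.2 expects withdrawal to be uncommon, and treatment is one self-applied tablet with matching placebo. At 3% versus 5% the effect is close to simulation error, and 5% versus 15% is a stress case. This stands as to size; the contradiction remains.

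**Carrying dropouts to the horizon is a usable worst-case convention.** It is, if labelled as one, and the SAP does not label it. Nor is it always conservative: more loss on placebo produces apparent benefit.

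**Time to cessation contradicts nothing in the protocol.** Correct. Protocol 9.4.4 has no censoring rule, so a charge of protocol deviation would be wrong for that endpoint. The fault there is the rule itself.

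**The missing-date sentences need not reach dropouts.** A reader might infer that Section 4 imputes 336 h for every dropout's DOE, or deletes every dropout's time to cessation. The text does not establish this. A healing end date presupposes healing, as SAP 3.3 says outright, and the cessation sentence follows one that already settles participants without cessation. For dropouts this is an ambiguity, not a certain error. The conflicts for participants with the event do not depend on that reading.

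**Conclusion.** The contradiction for DOE is certain from the text, is undeclared, and needs no assumption. The same fixed horizon for time to cessation is a weakness of the SAP rule, not a departure from the protocol. Three ITT analyses are exposed, and PP is largely protected from the censoring rule. The missing-date conflicts are a separate, textual fault, and the missing-hour one can affect PP.

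The size cannot be fixed from the documents, because the sample size is redacted and no loss rate is given. All simulated figures rest on the assumed distribution, sample size and loss pattern. They show that the effect is nil or small with little loss, a dilution with equal loss, and a material bias in either direction with clearly unequal loss. The very high rejection rates need all loss to precede healing as well as a large imbalance, and nothing in the documents points to either. This should be fixed before the ITT analyses are relied on.

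**What to change.** In SAP Section 4, for both endpoints, censor participants without the event at the earlier of 14*24 h and the last assessment at which they are known not to have had it:
- vesicular lesions: the last evaluable face image;
- non-vesicular lesions: the latest assessment at which the image score is above 0, or any NRS score is above 0, or both components are known and the event is not met;
- time to cessation: the last NRS assessment.

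For missing dates:
- limit the 14*24 h imputation in SAP 3.3 and Section 4 to participants documented as healed or symptom-free whose event date is missing;
- apply one rule to both endpoints, and state whether the imputed value is an event or censored;
- keep the result missing for any participant whose treatment start date is missing;
- remove the reference to a missing time from the DOE imputation sentence, so that the missing-hour sentence governs when both dates are recorded.

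If the fixed 336 h rule is kept, label it a sensitivity analysis and declare it in SAP 7.13.

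The cost is small: a few sentences in SAP Section 4, alignment of SAP 3.3, possibly a line in SAP 7.13, and endpoint-specific censoring dates in the programming. No new data are needed.

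### SAP section 4 gives two DOE values, days × 24 and 336 h, when only the healing clock time is missing; SAP 3.3 and 4 also disagree in part on time to cessation

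*SAP*

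**What the plan says.** **DOE.** SAP section 4 (Duration of Episode) has two consecutive rules for incomplete records:

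- The first opens "If time (hour) is missing for either treatment initiation or the healing of primary lesion or both, however, both dates are recorded" and sets DOE to the difference in dates multiplied by 24.
- The second reads "If only healing ending date and/or time are missing, DOE will be imputed as 14*24 hours".

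DOE is set to missing in one situation only: "If date of treatment initiation is missing, then DOE will be missing". Participants who do not heal are handled separately: "the data will be censored at 14 days (14*24 hours) regardless of any circumstances".

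SAP 3.3 has its own rule with a narrower trigger: "For subjects whose HL lesions are healed, however, healing ending date and time are missing". The result covers two endpoints: "DOE and time to cessation of symptoms will be imputed as 14*24 hours".

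**Time to cessation of symptoms.** The SAP section 4 definition opens its rule for a missing hour with "If hour is missing for either treatment initiation or the endpoint but both dates are recorded" and again multiplies the difference in dates by 24. It then adds "If either date is missing, then Time to cessation of symptoms is missing".

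**The concern.** DOE feeds the log-rank test, the Kaplan-Meier medians and the Cox hazard ratio in SAP 7.7.1. Its derivation should give one value per record. For one pattern of missing data it gives two, and the SAP does not say which rule takes precedence. If the second is followed literally, a participant with a known healing date is analysed as though healing took the whole observation period.

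Time to cessation has a related fault. SAP 3.3 decides its value from the healing date, while section 4 decides it from the initiation and cessation dates. The same participant can be kept at 336 h under one section and dropped under the other.

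**Working it through.** **1. Which DOE records meet two rules.** Assume the initiation date is recorded.

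| Healing date | Healing time | Dosing time | Difference in dates × 24 | 336 h (section 4) |
|---|---|---|---|---|
| recorded | missing | recorded | applies | applies, through *and/or time* |
| recorded | missing | missing | applies | excluded by *only* |
| recorded | recorded | missing | applies | does not apply |
| missing | missing | recorded | does not apply | applies |

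Only the first row is in conflict. SAP 3.3 does not settle it, because that rule needs the healing date and the healing time both to be missing. Two other places show which wording is out of line: the narrower trigger in 3.3, and the use of days × 24 for the same pattern in time to cessation.

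**2. Gap between the two rules.** SAP 3.4 numbers the dosing date as Day 1, so the difference in dates is Day − 1. The imputed value is 14 × 24 = 336 h. Protocol section 2 describes the usual course of blisters as about 7 to 10 days. That is not time from dosing, so Days 8 and 11 below are illustrative.

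| Healing seen on | (Day − 1) × 24 | 336 minus this |
|---|---|---|
| Day 8 | 7 × 24 = 168 h | 168 h |
| Day 11 | 10 × 24 = 240 h | 96 h |
| Day 14 | 13 × 24 = 312 h | 24 h |

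**3. Error of each rule against the true time.** Protocol 8.1.5 schedules images and symptom scores at 09:00, 14:00 and 19:00, each ±60 minutes, so an assessment falls between 08:00 and 20:00. Dosing can be at any hour, 00:00 to 24:00.

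True time = (Day − 1) × 24 + assessment clock − dosing clock.

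- True time minus days × 24 runs from 8 − 24 = −16 h to 20 − 0 = +20 h, on any day.
- Day 8: true time 152 to 188 h, so 336 h is too long by 148 to 184 h.
- Day 11: true time 224 to 260 h, so 336 h is too long by 76 to 112 h.
- Day 14: true time 296 to 332 h, so 336 h is too long by 4 to 40 h.

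**4. Scale for the trial, by assumption only.** The documents give no rate of missing times, and the sample size is redacted. As an illustration, assume gamma-distributed DOE (mean 120 h, shape 6, capped at 336 h) with times missing at random in one pooled sample:

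| Records lacking the healing time | Median, days × 24 | Median, 336 h |
|---|---|---|
| 2% | 113.3 h | 114.4 h |
| 5% | 113.4 h | 116.2 h |
| 20% | 114.4 h | 128.8 h |

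This says nothing about the difference between arms.

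**5. Time to cessation, healed participant with a recorded initiation date.**

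| Healing date and time | Cessation date | SAP 3.3 | SAP section 4 |
|---|---|---|---|
| missing | missing | 336 h | missing |
| missing | recorded | 336 h, read literally | from the recorded date |
| recorded | missing | not triggered | missing |

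The first row is a direct clash. In the second, a literal reading of 3.3 overwrites a recorded cessation date because a different date is absent.

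**The case against.** The best defence is that the intended reading can be recovered. The days × 24 sentence is the specific rule, and the 336 h sentence can be taken to cover what remains, a missing healing date. SAP 3.3 and the time-to-cessation definition support that reading. Affected records should also be few: healing is read from scheduled platform images, and the per-protocol population, which is primary, requires 14 days of evaluations. Both arguments stand as to weight. They do not remove the overlap, since no precedence is written. The ITT population, in which DOE is also analysed, has no 14-day requirement.

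A reader might infer more than the text supports:

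- *Every record without a healing time is in conflict.* It is not. If the dosing time is missing too, *only* takes the record out of the 336 h rule.
- *Every missing cessation date produces a clash.* It does not. SAP 3.3 is confined to healed participants who lack the healing date and time.
- *336 h for a healed participant without a healing date is a contradiction.* It is not. SAP 3.3 and section 4 agree on it. The value equals the censoring time for unhealed participants and exceeds the latest scheduled image (13 × 24 + 20 = 332 h), but describing the participant as healed implies an event. Event or censored status at 336 h cannot change a Kaplan-Meier median below 336 h. One clause stating the status is enough.
- *The primary comparison is biased.* Nothing in the documents shows that missing healing times would differ between arms.

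**Conclusion.** The point holds for one exact DOE pattern: both dates and the dosing time recorded, healing clock time missing. The two rules then differ by 168, 96 and 24 h on Days 8, 11 and 14, and the 336 h rule discards a recorded date. The error bounds assume assessments taken within their scheduled windows and dosing at any hour.

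For time to cessation, an *other* endpoint analysed on ITT only, the sections conflict when a healed participant has neither date. SAP 3.3 read literally also overrides a recorded cessation date when the healing date and time are missing.

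The effect on the trial result cannot be computed and is probably small. The text should still be corrected before database lock, because it defines the primary endpoint and the correction is cheap.

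**What to change.** **DOE, SAP section 4.** Replace the two sentences with rules to this effect:

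1. Both dates known, at least one clock time absent: DOE = (end date − start date) × 24.
2. Initiation date known, healing date absent (with or without its time), participant known to have healed: take the healing date from the first dated assessment that meets the section 4 definition of healing. For a vesicular lesion this is the first dated image scored 0 or 1 after a score of 3 or more. Otherwise it is the later of the first dated image scored 0 and the first dated NRS assessment with all scores 0. If that assessment has no clock time, rule 1 applies.
3. No such dated assessment: DOE = 336 h, counted as an event.

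Simply deleting *and/or time* would not be enough. The remaining sentence would not clearly cover a date and time that are both absent. Align the DOE part of SAP 3.3 with these rules.

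**Time to cessation, SAP 3.3 and section 4.** State one rule in both places, keyed to the cessation date (the first dated NRS assessment with all scores 0) and not to the healing date, so that a recorded cessation date is never overwritten. Give a single rule for when no cessation date exists.

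**Cost.** SAP wording and minor programming, with no new data. Days × 24 remains approximate to within about a day. The group with no dated healed assessment should be nearly empty, so it needs no separate sensitivity analysis.
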